8.2 Populations for Analyses

- Intent-to-treat (ITT) analysis population: all randomized subjects who receive at least one dose of study medication. Analyses using the ITT analysis population will group the subjects according to the treatment group to which they are randomized.
- Per-protocol (PP) analysis population: all randomized subjects who receive at least one dose of study medication, excluding the subjects with relevant protocol deviations. Analyses using the PP analysis population will group the subjects according to the treatment group to which they are randomized.
- As-treated analysis population: all subjects who receive at least one dose of study medication. Analyses using the as treated analysis population will group the subjects on an as-randomized basis unless the subject received the incorrect medication for the entire period of treatment. In that case, the subject will be analyzed in the treatment group associated with the incorrect medication they received (“as-treated”).
- Cumulative abatacept population: all randomized subject who receive at least one dose of abatacept during the double-blind and/or the open-label period. All subjects of the ‘As-treated population’ will be included, except placebo subjects who never entered the open-label period.
- Immunogenicity analysis population: all subjects who receive at least one dose of study medication and who had at least 1 immunogenicity result reported after start of study medication.
- Full PK analysis population: all subjects who received at least one dose of abatacept study medication and who had at least 1 PK result reported after start of this study medication.
- Evaluable PK analysis population: this population is a subset of the PK analysis population and consists of the evaluable subjects for PK analysis. For all PK summaries and plots, a subject is evaluable for PK analysis at a specific day if the predose PK measurements were collected in the 4 to 10 days window after the previous SC abatacept dose and prior to the dose of the specific day.

8.3 Endpoints

8.3.1 Primary Endpoint(s)

The mean change from baseline (Day 1) in ESSDAI at Day 169.

8.3.2 Secondary Endpoint(s)

Key Secondary Endpoints

- The mean change from baseline in ESSPRI at Day 169.
- The mean change from baseline in the stimulated whole salivary flow at Day 169 among subjects with stimulated whole salivary flow of at least 0.1 mL/min at both screening and baseline.

Other Secondary Endpoints

[figure not shown]
- The mean change from baseline at all measured time points up to Day 169 in the DAS28-CRP among those with a tender plus swollen joint count ≥ 3 at baseline, among those with a tender plus swollen joint count < 3 at baseline and in the full population.
- The mean change from baseline at all measured time points up to Day 169 in the individual components of DAS28-CRP among those with a tender plus swollen joint count ≥ 3 at baseline, among those with a tender plus swollen joint count < 3 at baseline and in the full population.
- Proportion of subjects who achieve a minimally clinically important change (of at least 3 points) in the ESSDAI at all measured time points up to Day 169 in the full population, among those with stimulated whole salivary flow of at least 0.1 mL/min at both screening and baseline, and among those with stimulated whole salivary flow of less than 0.1 mL/min at screening or baseline.
- Proportion of subjects who achieve a minimally clinically important change (of at least 5 points) in the ESSDAI at all measured time points up to Day 169 in the full population, among those with stimulated whole salivary flow of at least 0.1 mL/min at both screening and baseline, and among those with stimulated whole salivary flow of less than 0.1 mL/min at screening or baseline.
- Proportion of subjects who achieve a minimally clinically important change (of at least 1 point) in the ESSPRI at all measured time points up to Day 169 in the full population, among those with stimulated whole salivary flow of at least 0.1 mL/min at both screening and baseline, and among those with stimulated whole salivary flow of less than 0.1 mL/min at screening or baseline.
- The mean change from baseline at all measured time points up to Day 169 in the ESSDAI in the full population, among those with stimulated whole salivary flow of at least 0.1 mL/min at both screening and baseline, and among those with stimulated whole salivary flow of less than 0.1 mL/min at screening or baseline.
- The mean change from baseline at all measured time points up to Day 169 in the ESSPRI in the full population, among those with stimulated whole salivary flow of at least 0.1 mL/min at both screening and baseline, and among those with stimulated whole salivary flow of less than 0.1 mL/min at screening or baseline.
- The mean change from baseline in the individual components of the ESSDAI at all measured time points up to Day 169 in the full population, among those with stimulated whole salivary flow of at least 0.1 mL/min at both screening and baseline, and among those with stimulated whole salivary flow of less than 0.1 mL/min at screening or baseline.
- The mean change from baseline in the individual components of the ESSPRI at all measured time points up to Day 169 in the full population, among those with stimulated whole salivary

flow of at least 0.1 mL/min at both screening and baseline, and among those with stimulated whole salivary flow of less than 0.1 mL/min at screening or baseline.

- The mean change from baseline in Schirmer's test at all measured time points up to Day 169.
- The mean change from baseline in ocular staining score at all measured time points up to Day 169.
- The mean change from baseline in tear break-up time at all measured time points up to Day 169.
- The mean change from baseline in unstimulated whole salivary flow at all measured time points up to Day 169 in the full population, among those with stimulated whole salivary flow of at least 0.1 mL/min at both screening and baseline, and among those with stimulated whole salivary flow of less than 0.1 mL/min at screening or baseline.
- The mean change from baseline in stimulated whole salivary flow at all measured time points up to Day 169 in the full population, among those with stimulated whole salivary flow of at least 0.1 mL/min at both screening and baseline, and among those with stimulated whole salivary flow of less than 0.1 mL/min at screening or baseline.
- The mean change from baseline in patient symptoms using the Numeric Rating Scale (NRS) for mouth dryness at all measured time points up to Day 169 in the full population, among those with stimulated whole salivary flow of at least 0.1 mL/min at both screening and baseline, and among those with stimulated whole salivary flow of less than 0.1 mL/min at screening and baseline.
- The mean change from baseline in patient symptoms using the Numeric Rating Scale (NRS) for eye dryness at all measured time points up to Day 169.
- The mean change from baseline in subject assessment of disease activity at all measured time points up to Day 169.
- The mean change from baseline in the physician global assessment of disease activity at all measured time points up to Day 169.
- The mean change from baseline in patient fatigue using PROMIS Fatigue assessment at all measured time points up to Day 169.
- The mean change from baseline in female sexual function using the FSFI at all measured time points up to Day 169.
- The mean change from baseline in patient function using SF-36 at all measured time points up to Day 169.
- Geometric mean of trough concentration (C_{min}) of abatacept at all measured time points.
- Proportion of subjects with at least one positive immunogenicity response up to Day 169 and during 3 months follow up (for subjects who discontinue during the 6-months double-blind)

and during the cumulative abatacept period and 3 months follow-up (for the cumulative abatacept population).

- Safety (proportion of subjects with adverse events, deaths, SAEs, and AEs leading to discontinuation and proportion of laboratory marked abnormalities) up to Day 169 and during the cumulative abatacept period and follow-up period.

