3.5 Discontinuation of Study Therapy

Subjects who discontinue treatment with investigational product during the Double-Blind Treatment Period must continue to be assessed for all efficacy measures and for safety at all remaining double-blind study visits through Week 24 (Day 169) (see [Table 5.1-2](#)). Those subjects who discontinue treatment with the study drug during the double-blind period will also require visits to assess safety and immunogenicity at 28 and 84 days after the last dose of study drug. If these visits fall within ± 14 days of a scheduled double-blind study visit, only an additional laboratory assessment (immunogenicity) needs to be performed at the scheduled study visit. Otherwise, the follow-up visits need to be performed.

Subjects who discontinue study drug during the Open-Label Treatment period should comply with protocol specified follow-up procedures as outlined in [Section 5](#). The only exception to this requirement is when a subject withdraws consent for all study procedures including post-treatment study follow-up or loses the ability to consent freely (ie, is imprisoned or involuntarily incarcerated for the treatment of either a psychiatric or physical illness).

Subjects MUST discontinue investigational product (and non-investigational product at the discretion of the investigator) for any of the following reasons:

- Subject's request to stop study treatment
- Any clinical adverse event (AE), laboratory abnormality or intercurrent illness which, in the opinion of the investigator, indicates that continuation of study therapy is not in the best interest of the subject
- Pregnancy
- Missed Doses:
 - During the double-blind period, any subject who misses greater than four consecutive doses or greater than eight total doses must be discontinued from study therapy
 - During the open-label period, any subject who misses greater than six consecutive doses or greater than ten total doses must be withdrawn from the study
- Significant non-compliance with protocol (ie, procedures, assessments, medication, etc). The investigator should discuss such issues with the BMS Medical Monitor.
- Use of prohibited medication. The investigator should discuss the use of a prohibited medication with the Medical Monitor prior to withdrawing a subject from study therapy

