6.1.1 Serious Adverse Event Collection and Reporting

Sections 5.5.1 in the Investigator Brochure (IB) represent the Reference Safety Information to determine expectedness of serious adverse events for expedited reporting. Following the subject's written consent to participate in the study, all SAEs, whether related or not related to study drug, must be collected, including those thought to be associated with protocol-specified procedures. All SAEs must be collected that occur during the screening period and within 84 days of discontinuation of dosing. If applicable, SAEs must be collected that relate to any later protocol-specified procedure (eg, a follow-up skin biopsy).

The investigator must report any SAE that occurs after these time periods and that is believed to be related to study drug or protocol-specified procedure.

An SAE report must be completed for any event where doubt exists regarding its seriousness.

If the investigator believes that an SAE is not related to study drug, but is potentially related to the conditions of the study (such as withdrawal of previous therapy or a complication of a study procedure), the relationship must be specified in the narrative section of the SAE Report Form.

SAEs, whether related or not related to study drug, and pregnancies must be reported to Sponsor or designee within 24 hours of awareness of the event. SAEs must be recorded on the SAE Report Form; pregnancies on a Pregnancy Surveillance Form (electronic or paper forms). The preferred method for SAE data reporting collection is through the eCRF. The paper SAE/pregnancy surveillance forms are only intended as a back-up option when the eCRF system is not functioning. In this case, the paper forms are to be transmitted via email or confirmed facsimile (fax) transmission to:

SAE Email Address: Refer to Contact Information list.

SAE Facsimile Number: Refer to Contact Information list.

For studies capturing SAEs through electronic data capture (EDC), electronic submission is the required method for reporting. In the event the electronic system is unavailable for transmission, paper forms must be used and submitted immediately. When paper forms are used, the original paper forms are to remain on site.

SAE Telephone Contact (required for SAE and pregnancy reporting): Refer to Contact Information list.

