8.4.3 Safety Analyses

The proportion (%) of subjects with adverse events, deaths, SAEs, and AEs leading to discontinuation and subjects with laboratory marked abnormalities up to start of open label for subjects continuing in the OL or up to last dosing date +56 days for subjects discontinuing during double blind will be provided per treatment group using the as-treated population. These safety endpoints will also be summarized during the cumulative abatacept period (from the first day of abatacept treatment in the study up to 56 days after the last abatacept treatment in the study) for the cumulative abatacept population. For the cumulative abatacept population all subjects will be combined in one group.

The proportion (%) of subjects with at least one positive immunogenicity response (relative to baseline) up to Day 169 and 3 months follow up (for subjects who discontinue in the Day 169 short-term period) and during the cumulative abatacept period and 3 months follow-up (for the cumulative abatacept population) will be summarized using the immunogenicity population.

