eye drops must not be used for 8 hours prior to Day 1 and prior to the day of quarterly eye assessments. The use of ophthalmic and oral lubricants should not be used on Day 1 or on the day of the quarterly salivary and eye assessments (prior to the assessments). Study procedures will occur as specified in protocol Table 5.1-1.

Double-Blind Treatment Period:

On day 1, subjects will be randomized to one of two blinded treatment arms in a 1:1 ratio:

- Abatacept 125mg for subcutaneous administration weekly
- Matching placebo for subcutaneous administration weekly

The duration of the Double-Blind Treatment Period is 169 days. Abatacept (125mg) or matching placebo will be administered subcutaneously (SC) once per week. During this period, the dose of oral corticosteroids ($\leq 10\text{mg/day}$ or equivalent), hydroxychloroquine, pilocarpine, cevimeline, cyclosporine eye drops, lifitegrast, autologous serum eye drops, oral and ocular lubricants and/or NSAIDs should remain stable. Analgesics are permitted with certain restrictions (see protocol Section 3.4.1.2). Study procedures will occur as specified in protocol Table 5.1-2, 5.1-4, 5.1-5.

Subjects who discontinue treatment with study drug during the Double-Blind Treatment Period must continue to be assessed for all efficacy measures and for safety at all remaining double-blind study visits through Week 24 (Day 169). In addition, subjects who discontinue treatment with the study drug will require visits to assess safety 28, 85 and 169 days after the last dose of study drug, and immunogenicity 85 and 169 days after the last dose of study drug. If these visits will fall within ± 14 days of a scheduled study visit, only an additional laboratory assessment (immunogenicity) may need to be performed at the scheduled study visit. Otherwise, the follow-up visits 28, 85, and/or 169 days after last dose of study medication need to be performed at the appropriate time.

Open-Label period:

[figure not shown]

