6 STUDY PERIODS, TREATMENT REGIMENS AND POPULATIONS FOR ANALYSES

6.1 Study Periods

In this study, there are five study periods: Screening period, Double-Blind Period, Open-Label Period, Cumulative Abatacept Period and Follow-up Period. The following analysis periods defined below are for analysis purposes. The definitions below indicate the data to be included in the analysis of each specified period.

- **Screening period:** It covers the time period which starts from the day of enrollment and lasts until the initiation of the randomized Double-Blind Period.
- **Double-Blind Treatment Period:** It starts at the time of the first dose of blinded treatment and continues up to 56 days post last dose in the Double-Blind Period or prior to the first dose in the open-label period, whichever is earlier for safety (AE and laboratory summaries). Up to 42 days post last dose in the Double-Blind Period or prior to the first dose in the open-label period, whichever is earlier for efficacy analyses. Up to 21 days post last dose in the Double-Blind Period or prior to the first dose in the open-label period, whichever is earlier for on-treatment immunogenicity summaries.
- **Open-Label period:** It starts at the time of the first dose of open-label treatment and continues up to 56 days post last dose for safety (AE and laboratory summaries). Up to 42 days post last dose for efficacy analyses and up to 21 days post last dose for the on-treatment immunogenicity summaries.
- **Cumulative Abatacept Period:** It starts at the time of the first dose of abatacept (either in the Double-Blind Period for the subjects randomized to abatacept or in the open-label period for the subjects randomized to placebo) and continues up to 56 days post last dose of abatacept for safety (AE and laboratory summaries) and up to 21 days post last abatacept dose for the on-treatment immunogenicity summaries. The last abatacept dose can be last dose in Double-Blind Period for subjects not treated in the open-label period.
- **Follow-up Period:** immunogenicity summaries are provided for the follow-up period that starts at Day 22 post last dose and continues up to last assessment of immunogenicity in the study.

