7.6 Safety

The safety analysis endpoints described in this section are considered as secondary endpoints. For their analysis, there will be no statistical testing of group differences.

Analysis of all safety data will follow the BMS standard safety data conventions³ and abatacept program safety conventions⁴.

All summaries of safety parameters during the Double-Blind Treatment Period will be provided by treatment groups. All safety assessments will be included in the summary tables if the onset date is on or after the first dose date and up to 56 days post the last dosing day in the Double-Blind Treatment Period or the first dosing date in the open-label period, whichever occurs first. Presentations for the Double-Blind Treatment Period will be provided by “as treated” treatment group for the as-treated analysis population, unless otherwise specified.

These safety endpoints will also be summarized during the cumulative abatacept period (from the first day of abatacept treatment in the study up to 56 days after the last abatacept treatment in the study) for the cumulative abatacept population. For the cumulative abatacept population all subjects will be combined in one group.

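### The safety endpoint runs to Day 169 and through follow-up, but every AE, SAE and laboratory summary stops at or before 56 days after last dose, so part of the defined span is not tabulated

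*Protocol*

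**What the plan says.** **Endpoint.** Protocol 8.3.2 (and the synopsis) lists safety as a secondary endpoint: the proportions with AEs, deaths, SAEs and discontinuation due to AEs, "and proportion of laboratory marked abnormalities) up to Day 169 and during the cumulative abatacept period and follow-up period".

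**Analysis windows.** Protocol 8.4.3 gives the by-arm proportions to the start of open label, or "up to last dosing date +56 days for subjects discontinuing during double blind". Its cumulative abatacept summary ends 56 days after the last abatacept dose. SAP 7.6 applies the same limit to the double-blind tables: "up to 56 days post the last dosing day in the Double-Blind Treatment Period or the first dosing date in the open-label period", taking the earlier of the two. SAP 6.1, 7.6.1, 7.6.3 and 7.6.3.1 repeat the 56-day limit, and SAP 8.5 admits only safety assessments within 56 days of last dose for subjects who stop drug. The malignancy, autoimmune, injection-reaction, SAE and exposure-adjusted tables (SAP 7.6.2) use only the double-blind and cumulative abatacept periods, both capped in this way. For the Follow-up Period, SAP 6.1 says that "immunogenicity summaries are provided for the follow-up period that starts at Day 22 post last dose"; it names no AE or laboratory summary.

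**Collection.** Under Protocol 3.5, subjects who stop drug in the double-blind period "must continue to be assessed for all efficacy measures and for safety at all remaining double-blind study visits through Week 24 (Day 169"). Protocol 6.1.1 says: "All SAEs must be collected that occur during the screening period and within 84 days of discontinuation of dosing". Protocol Table 5.1-6 schedules AE assessment 28 and 84 days after last dose. SAP 2.1 goes further: "subjects who discontinue treatment with the study drug will require visits to assess safety 28, 85 and 169 days after the last dose".

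**The concern.** The plan asks sites to collect safety data that no planned safety table uses, and the endpoint claims to cover that time. Two stretches are affected.

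- **Before Day 169.** The randomised comparison of safety is cut at a point that depends on when each subject stopped drug. SAP 7.6.1 divides by everyone who received at least one dose. An early discontinuer therefore stays in the denominator while events after day 56 off drug do not reach the numerator. If discontinuation timing differs between arms, the proportions are affected unequally.
- **After the final dose.** AEs and SAEs late in follow-up, malignancies and infections among them, enter no proportion or rate.

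The contrast with other data suggests an omission. Immunogenicity has its own follow-up summaries. Efficacy has analyses using on- and off-treatment measurements to Day 169, subject to missing-data thresholds (SAP 7.1.5, items 3 and 4). Safety has no counterpart to either.

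**Working it through.** **Basis of the 56 days.** SAP 7.4.1 describes the offset as about 4 half-lives. Protocol 3.3.1 equates 5 half-lives with 70 days, so the half-life is 70 / 5 = 14 days, and 56 / 14 = 4. The stated basis reproduces.

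**Gap 1: double-blind discontinuers, up to Day 169.** Inputs: required assessment to Day 169 (Protocol 3.5); summary end at last dose + 56 (Protocol 8.4.3, SAP 7.6). With last dose on Day d, the days left out are

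169 - (d + 56) = 113 - d, or 0 if d is 113 or later.

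Weekly dosing from Day 1 puts double-blind doses on Days 1, 8, ..., 162.

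| Last dose (Day d) | Summary ends (d + 56) | Days left out before Day 169 |
|---|---|---|
| 1 | 57 | 112 |
| 29 | 85 | 84 |
| 57 | 113 | 56 |
| 85 | 141 | 28 |
| 106 | 162 | 7 |
| 113 or later | 169 or later | 0 |

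On schedule, Day 106 is the last dose day with a gap. Subjects who enter open label on schedule have no gap before Day 169.

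**Gap 2: after the final dose.** Counting from last dose, as Protocol Table 5.1-6 does:

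- Protocol follow-up of 84 days: 84 - 56 = 28 days; 28 / 84 = 33%.
- SAP follow-up of 169 days: 169 - 56 = 113 days; 113 / 169 = 67%.

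Protocol 3.1.4 and the follow-up paragraph of SAP 2.1 count instead from the last treatment visit for subjects who complete. That start is not before the last dose, so these gaps are not overstated for them.

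**What is reported beyond 56 days.**

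| Data | Summary (proportion or rate) | Other reporting |
|---|---|---|
| Deaths | None specified | All recorded deaths reported, with narratives; fatal AEs listed (SAP 7.6.2.5); no window stated |
| SAEs | None | All SAEs listed (SAP 7.6.2.6) |
| AEs | None | Subject listings |
| Routine laboratory tests | None | Table 5.1-6, as shown, schedules only pregnancy, anti-abatacept antibody and PK samples |

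The laboratory gap is therefore mainly the off-treatment double-blind visits in Gap 1.

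**What cannot be computed.** The documents give no discontinuation rate and no event rates, so neither the number of subjects in Gap 1 nor the number of events in either gap can be derived.

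**The case against.** The best defence is that 56 days is a legitimate on-treatment window. The protocol's own analysis section sets it in advance, the SAP applies it consistently, and a pharmacokinetic reason is given. Safety is descriptive, with no testing between groups (SAP 7.6). SAP 7.6.2.8 adds rates per 100 patient-years, which allow for unequal observation time. All of this stands as a case for keeping the window. It does not justify having that window alone for an endpoint defined more broadly, and exposure adjustment does not bring back events that fall outside the window.

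There are also limits on what can be verified. The supplied protocol's visible history ends at Amendment 01, while the SAP describes Amendments 6 and 8 and a longer follow-up. The SAP's endpoint list is blacked out before its safety entry, and the sponsor's safety conventions are not supplied. This tempers confidence about how the endpoint is now worded. The analysis windows in the SAP are fully visible.

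Three stronger readings are tempting but not supported:

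- **Late safety data are lost, deaths included.** Deaths are reported, narrated and listed with no stated cut-off, and all SAEs are listed. What is missing is a summary.
- **The 56 days should be at least 70, because the protocol uses 5 half-lives elsewhere.** The 70-day figure is a contraception margin (Protocol 3.3.1). It does not define an AE window.
- **The randomised safety comparison is displaced for the whole trial.** Only discontinuers with last dose before Day 113 lose time before Day 169.

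**Conclusion.** Wrong as written. The endpoint in Protocol 8.3.2 and the windows in Protocol 8.4.3 and SAP 6.1, 7.6 and 8.5 cannot both be followed. A report built to the SAP would not contain the proportions that the endpoint defines. The size is 113 - d days per early double-blind discontinuer (at most 112), plus 28 of 84 (protocol) or 113 of 169 (SAP) follow-up days for AEs and SAEs. This rests on the visible text only, on follow-up counted from last dose, and on the blacked-out SAP wording and sponsor conventions not adding a summary beyond 56 days. The effect on the trial's safety conclusions could be small; the documents do not allow it to be estimated.

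**What to change.** Keep the 56-day on-treatment tables unchanged. Add two descriptive summaries to SAP 6.1 and 7.6, and exempt them from the 56-day rule in SAP 8.5:

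- (a) By arm: AEs, SAEs, deaths and marked laboratory abnormalities from first dose to the earlier of the first open-label dose or Day 169/last contact, regardless of treatment discontinuation.
- (b) AEs, SAEs, deaths and malignancies with onset more than 56 days after last dose, up to last study contact, with person-time. Pool these for the cumulative abatacept population, and show placebo subjects who never received abatacept separately, since SAP 6.3 leaves them out of that population.

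Ending (b) at last contact makes it work under either follow-up length.

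The cost is SAP wording and two tables from data that sites must already collect. The drawback is that late events are less specific to drug, which is why they are shown apart from the on-treatment tables.
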